1. Patients found to be eligible for the study can be screened and enrolled anytime during first six weeks of radiation therapy. VAS pain scores will be recorded weekly using BPI questionnaires and daily using the pain app from the day of enrollment, as outlined in study calendar. Treatment with study regimen, collection of PROMIS[®], MDASI, CTCAE and other assessments like opioid drug use log, as outlined in the study calendar will start once the patient develops mucositis and has VAS \geq 4/10 pain score on the OM Pain App and BPI questionnaire (question 3: your pain at its worst in last 24 hours). Patients usually develop mucositis by the third or fourth week of radiation therapy so we anticipate treatment would begin by fourth week in most patients, but it may start sooner if the patient develops mucositis and has VAS \geq 4/10 pain. If a patient presents with radiation-induced mucositis pain on the day of enrollment, then, all study procedures, including PROMIS[®], MDASI-HN, and CTCAE will be completed that day. Visit procedures that were performed as standard of care prior to consent (without the specific intent to make the subject eligible for the trial), may count toward screening tests and eligibility if they are within the screening window of two days. Clinician follow-up will be scheduled weekly (1–7) and then on weeks 9 and 12.
2. If a subject is off the study drug regimen or the subject withdraws, then they will be followed as per follow-up requirements.
3. Serum chemistry values will include ALT/SGPT, AST/SGOT, alkaline phosphatase, bilirubin (total, direct, and indirect) creatinine, LDH, sodium, potassium, chloride, bicarbonate, calcium, phosphate, magnesium, BUN/urea, albumin, glucose. Serum chemistry results obtained from unscheduled visits should be entered into the electronic database. Additional serum

chemistry testing should be done as clinically indicated.

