3.2 Study Procedures

Patients found to be eligible for the study can be screened and enrolled anytime during the first six weeks of radiation therapy. VAS pain scores will be recorded weekly using the BPI questionnaires. They will also be recorded daily, using the pain app from the day of enrollment as outlined in study calendar. Treatment with the study regimen, collection of data from the PROMIS®, MDASI, CTCAE evaluation, and other assessments, such as the opioid drug use log as outlined in study calendar will start once patient develops mucositis and has VAS >4/10 pain score on the OM Pain App and the BPI questionnaire (question 3: your pain at its worst in last 24 hours). Patients usually develop mucositis by the third to fourth week of radiation therapy so we anticipate treatment would begin by fourth week in most patients, but it can start sooner if the patient develops mucositis and has VAS≥4/10 pain. If a patient presents with radiation-induced mucositis pain on the day of enrollment, then, all study procedures, including administering the PROMIS® and MDASI-HN questionnaires, in addition to CTCAE evaluation, will be completed on that day. Visit procedures that were performed as standard of care prior to consent (without the specific intent to make the subject eligible for the trial), may count toward screening tests and eligibility if they are within the screening window of two days. Clinician follow-up will be scheduled weekly (weeks 1–7) and then on weeks 9 and 12. Data can also be collected over phone during the follow-up period (weeks 8–12 from the start of radiation therapy). If a subject stops radiation therapy within the first 7 weeks, weekly visits will continue as scheduled if he/she is on treatment.

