5.9 OM Pain App

5.9.1 Device Description/Overview

The Oral Mucositis (OM) Pain App is a smartphone application that was designed to permit patients to key in pain severity using a visual analog 0–10 scale. The app is programmed with an alarm to prompt the patient to record pain severity at prescribed intervals daily and through spontaneous patient input. Time intervals for prompted pain queries can be customized, when, for instance, patients work a night shift or have specific sleep/wake cycle preferences.

Deidentified data collected on each patient's smartphone will be transferred wirelessly to cloud storage. Data transmitted wirelessly will use HTTP secure (HTTPS) sessions and JSON/XML protocols, such as the security used in online banking. Security measures and only deidentified data will be transmitted. Study participants will be encouraged not to update the smartphone operating system during the conduct of the study. Study PIs and/or study coordinator will perform OM Pain App software updates on smartphones.

Analysis of data collected from smartphones will be performed from cloud-stored data on deidentified sources only. This would be done in collaboration with our co-investigators at University of Wisconsin Milwaukee (UWM). The raw pain scores will be used to generate a time-weighted measure of pain called total area under the pain curve (AUC). Average weekly pain scores will also be calculated. This is a summary measure that integrates serial assessments of a patient's pain over the duration of the study. Architecture of the pain app is illustrated in figures 1 and 2.

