8 STATISTICAL CONSIDERATIONS

8.1 Study Endpoints

8.1.1 Primary endpoint: Establish efficacy of study regimen by showing that at least 33% of patients will achieve at least a 30 percent decrease in VAS pain score from baseline to the end of week 9 of treatment and follow-up period. Earlier studies have shown that the VAS pain score ($\geq 4/10$) on the day of treatment initiation can be used as baseline in this setting and a 30% or higher reduction in baseline pain score is a sign of meaningful drug response.(27-29)

8.1.2 Secondary endpoint:

1. Monitor compliance of study drug regimen through OM Pain App and medication diary.

2. Identify study participants who require off-protocol opioids for pain control despite being on the highest dose of study drug combination.
3. Correlate cumulative mean weekly pain scores calculated by the pain app with the average weekly pain scores recorded by the BPI short form.
4. Correlate average weekly OM Pain App scores and average weekly pain scores calculated from the BPI short form with head and neck symptoms and function evaluation tool MDASI-HN. The cumulative average area under the curve (AUC) weekly pain scores are expected to be inversely proportion to MDASI-HN average weekly AUC physical activity scores.
5. Maintain a weekly log of use of other nonopioid supportive care medications, such as laxatives, antiemetics, and oral anesthetics, in conjunction with the study drug combination during treatment and follow-up period through weekly questionnaires. Average weekly use of laxatives and antiemetics is expected to decrease by the end of follow up period.
6. Assess incidence and severity of gastrointestinal and cognitive side effects of the study drug regimen and their impact on quality of life, as measured by weekly PROMIS® (GI and cognition) questionnaires.
7. Safety: Assess the incidence and severity of other adverse events associated with the study drug combination using CTCAE version 5.

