8.6 Data Analysis

Serial measurements of patient-reported pain data will be analyzed throughout the follow-up period to look for inadequate pain control and use of off-protocol breakthrough pain medication use. The pain app data will be analyzed by study coordinators and our collaborators at UWM. Data recording will commence on the day the patient starts taking the drug regimen. We plan to study the daily and weekly pain score patterns during therapy. We will determine the baseline VAS pain score on the day of treatment initiation. Other pain management studies in radiation-induced mucositis acknowledged the fact that the pain curve follows a nonlinear pattern during radiation therapy, but it plateaus and later drops down to a lower level after initiation of long-acting effective pain medications. Hence, it is reasonable to use the pain score on the day of treatment initiation as our baseline pain score. (29, 31) Radiation-induced mucositis begins to heal approximately two weeks after the last dose of stomatotoxic chemotherapy or radiation therapy.(30, 32) We will assess a percentage drop in the pain score by the end of week 9 of treatment to show a drug response. This way, we will try to avoid any bias of the normal healing process on pain alleviation. At least two-week treatment with study drug regimen will be required in order to be considered evaluable for study endpoints. Earlier studies and consensus guidelines have shown that a 30% drop in average weekly pain score by end of the follow-up period is significant. (28). The recording of data will cease after 12 weeks, at which time mucositis-related pain symptoms substantially abate in many individuals. (32)

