The primary analysis will compare the proportion of patients achieving a 30% drop in pain scores to the null-hypothesis value of 33% at a one-sided 5% significance level using a binomial test. The number of patients using analgesic and non-analgesic medications, as well as the occurrence of adverse events, will be tabulated and presented as counts with percentages. The average weekly pain scores, MDASI-HN, and the PROMIS® measures will be reported with descriptive statistics (mean, standard deviation, median, and range). Patient level summaries of the pain score and PRO outcomes will be created by computing area under the curve (AUC) of weekly averages. Scatterplots will be used to explore their relationship which will be quantified by Spearman's correlation coefficient. Further correlational analysis will be done by linear regression and linear fixed models.

8.7 Rationale for not Having a Stopping Rule: This is a supportive care pilot study to determine

the efficacy of transdermal buprenorphine and oral tramadol drug combination in alleviating radiation-induced mucositis pain in head and neck cancer patients. These pain medications are FDA approved and have an established safety profile. In addition to the primary efficacy endpoint, we will be evaluating other secondary end points, such as real-time pain monitoring through the OM Pain App. This will continue, even if the study drug regimen is discontinued for lack of efficacy or some other unspecified reason. This would provide us invaluable pilot data for future studies in this setting. Moreover, we have made provisions for switching to standard-of-care pain medications, such as oral oxycodone in our study for patients who don't derive adequate pain relief from the study regimen. Hence, it is reasonable to exclude a formal stopping rule for this trial.

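### Section 8.6 correlates patient-level AUCs without standardising for weeks observed, and the AUC scale is described inconsistently; read as a total, it biases the pain–PRO correlation upward

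*Combined protocol and SAP*

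**What the plan says.** The analysis instruction is in Section 8.6: "Patient level summaries of the pain score and PRO outcomes will be created by computing area under the curve (AUC) of weekly averages". The relationship between the summaries is explored by scatterplot and "quantified by Spearman's correlation coefficient", followed by regression models. This serves secondary endpoint 4 (Sections 2.5 and 8.1.2): "Correlate average weekly OM Pain App scores and average weekly pain scores calculated from the BPI short form" with the MDASI-HN.

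The scale of the AUC is not the same throughout:

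- Section 5.9.1 describes a total: "The raw pain scores will be used to generate a time-weighted measure of pain called total area under the pain curve (AUC". Sections 1.5.4 and 5.1 also speak of a total AUC.
- Secondary endpoint 4 speaks of a cumulative average AUC for pain and expects it to be "inversely proportion to MDASI-HN average weekly AUC physical activity scores". Section 5.1 also uses a mean weekly AUC pain score.

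The start of recording also differs between sections:

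- Section 3.2 says that study treatment, PROMIS, MDASI and other assessments "will start once patient develops mucositis and has VAS >4/10 pain score on the OM Pain App" and the BPI.
- Section 8.6 says "Data recording will commence on the day the patient starts taking the drug regimen", and Section 5.9.3 likewise ties formal monitoring to the start of the regimen.
- Study calendar footnote 1 says "VAS pain scores will be recorded weekly using BPI questionnaires and daily using the pain app from the day of enrollment".

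Recording ends at week 12. The calendar counts weeks from the first week of radiation, without adjustment for treatment start.

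**The concern.** The observation window differs between patients by design. Section 4.10 allows treatment to start at any point in the first six weeks of radiation, and the end is fixed on the radiation clock. A total AUC is roughly the mean level multiplied by the weeks spanned. If pain and a PRO are both totalled over the same window, a patient observed longer ranks higher on both, whatever the scores are. Ranking does not remove this.

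The artefact is positive whichever way a scale points. Endpoint 4 expects an inverse relation between pain and physical activity, so a total AUC would pull the estimate towards zero or past it. For symptom scales, where a positive relation is natural, it would inflate the estimate. Instruments whose minimum is above zero are most exposed. The PROMIS items in Appendix 4 score 1 to 5, so a raw-score AUC rises with time even in a patient without symptoms.

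**Working it through.** **Plan's own figure.** The documents give none for this correlation. The primary design does not use the AUC correlation, and its stated figures reproduce: at least 10 responders of 18, with rates 0.33 and 0.63, gives exact one-sided alpha 0.041 and power 0.816.

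**Step 1: unequal windows.** A start in week 2 gives 12 − 2 + 1 = 11 weekly values spanning 10 weeks. A start in week 6 gives 12 − 6 + 1 = 7 values spanning 6 weeks. Two patients with identical constant scores, pain 5 and PRO 4, illustrate the effect:

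| Start | Pain total AUC | PRO total AUC | Divided by weeks |
|---|---|---|---|
| Week 2 | 5 × 10 = 50 | 4 × 10 = 40 | 5 and 4 |
| Week 6 | 5 × 6 = 30 | 4 × 6 = 24 | 5 and 4 |

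**Step 2: approximate size.** Write total AUC = L × m, where L is weeks spanned and m is the patient's mean level. If the two levels are independent of each other and of L, the correlation of the log AUCs is approximately

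CV_L² / √[(CV_L² + CV_pain²)(CV_L² + CV_PRO²)].

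Assumed inputs are pain mean 5, SD 1.5 (CV 0.30), and either an MDASI-like score with mean 4, SD 2 (CV 0.50), or a PROMIS-like T-score with mean 52, SD 8 (CV 0.154).

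- Starts in weeks 3–4, no dropout, CV_L = 0.057. MDASI-like: 0.00325 / √(0.09325 × 0.25325) = 0.02. T-score-like: 0.00325 / √(0.09325 × 0.02692) = 0.06.
- Starts in weeks 2–6 around weeks 3–4, no dropout, CV_L = 0.126. MDASI-like: 0.0159 / √(0.1059 × 0.2659) = 0.09. T-score-like: 0.0159 / √(0.1059 × 0.0396) = 0.25.

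**Step 3: simulation.** Each scenario had 2,000 trials of n = 18 with independent pain and PRO levels. Trapezoid AUCs ran from treatment start to week 12, or to dropout at least 2 weeks after the start, without imputation. Pain SD was 1.5 (assumed) or 2.4 (Section 1.5.2, worst pain). Low ends are MDASI-like with pain SD 2.4. High ends are T-score-like with pain SD 1.5.

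| Start weeks | Dropout | Mean Spearman, total AUC | Two-sided p < 0.05 |
|---|---|---|---|
| 3–4 | none | 0.02–0.06 | 5–6% |
| 3–4 | 10% | 0.10–0.21 | 7–15% |
| 2–6, centred on 3–4 | none | 0.08–0.23 | 7–18% |
| 2–6, centred on 3–4 | 10% | 0.14–0.34 | 9–32% |
| 1–6, uniform | none | 0.14–0.41 | 9–42% |
| 1–6, uniform | 10% | 0.19–0.49 | 12–60% |

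The no-dropout rows for starts in weeks 3–4 and 2–6 agree with Step 2. With each AUC divided by its weeks, mean Spearman was −0.01 to 0.02 in every scenario and the rejection rate was 4.5% to 6.4%.

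**Step 4: masking.** Take a true patient-level correlation of −0.5, starts in weeks 2–6, 10% dropout, the MDASI-like score, pain SD 1.5 to 2.4 and within-patient SD 1.5. Total AUC then gave mean Spearman −0.14 to −0.23. AUC divided by weeks gave −0.41 to −0.44.

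**The case against.** A reader might infer that the plan commits to summed AUCs. The documents do not support that. Section 8.6 does not say whether the AUC is standardised, and the wording of endpoint 4, with one phrase in Section 5.1, points to a per-week scale, which would already be the remedy. What stands is that the operative analysis sentence gives no division by weeks, that Sections 1.5.4, 5.1 and 5.9.1 say total, and that the literal reading of 8.6 is the biased one.

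A reader might also infer that a large spurious correlation is likely. The upper figures need start weeks spread evenly over weeks 1–6, whereas Section 3.2 and calendar footnote 1 expect treatment by week 4 in most patients. The dropout rows omit the multiple imputation in Section 8.8, which could restore weeks lost to dropout. Stopping the study drug does not itself end data collection (Sections 4.11 and 5.2). Imputation cannot help with weeks before treatment start, because those are not missing data.

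The rejection rates should not be read as the error rate of a planned test. Section 8.6 uses the coefficient descriptively, and the 5% level belongs to the primary analysis.

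Nor does the artefact manufacture support for endpoint 4's stated expectation. It is positive and the expectation is inverse, so the harm there is masking.

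Finally, whether pain and PRO windows coincide is unsettled. Sections 8.6 and 5.9.3 give both series the same start, while calendar footnote 1 starts pain at enrolment. Different windows would make the length only partly shared, but the two summaries would then cover different periods.

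**Conclusion.** The point holds as an undefined and inconsistently described AUC scale whose literal reading in Section 8.6 biases a named secondary analysis. The mechanism follows from the planned windows. The size rests on assumptions about start weeks, score means and SDs, and dropout timing; only the worst-pain SD of 2.4 and the 10% dropout rate come from the documents. On those assumptions the spurious mean Spearman runs from negligible, when starts are tightly clustered and follow-up is complete, to about 0.1 to 0.2 with starts over weeks 2–6, and about 0.15 to 0.35 when 10% dropout is added without imputation. The analysis is exploratory and the primary binomial test does not use it. It should be corrected before analysis because the correction is simple and endpoint 4 depends on it.

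**What to change.** In Section 8.6, define each patient-level summary as the AUC of weekly averages divided by the number of weeks it spans. State that, for each patient, pain and PRO summaries are computed over the same weeks, from treatment start to the last assessment common to both. Say how gaps within that window are handled, including admissions (when Section 5.4 suspends monitoring), and whether the imputation in Section 8.8 applies to the weekly scores before the AUC is formed. Then align the total, cumulative average, mean weekly and average weekly wording in Sections 2.5, 5.1, 5.9.1 and 8.1.2 with that definition. The cost is a few sentences in an amendment. No extra data, visits or patients are needed.

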As noted earlier, radiation-induced mucositis begins to heal approximately two weeks after the last dose of stomatotoxic chemotherapy or radiation therapy.(30, 32) Hence, we will assess a percentage drop in pain score by the end of week 9 of treatment to show a drug response. This way we will be able to avoid any bias of the normal healing process on pain alleviation. Studies have also shown that painful mucositis continues four to five weeks after the termination of radiation therapy. Thus, we plan to continue the study drug regimen up to 12 weeks. (17) (32) Recording of data will cease after 12 weeks, at which time mucositis-related pain symptoms substantially abate in many individuals. Details on buprenorphine and tramadol dose determination and titration are included in Section 5.2 of this protocol. Post-marketing data of buprenorphine, other opioid studies, and clinical experience have shown that around 20 percent of the patients receiving transdermal buprenorphine may have inadequate pain control and require rescue off-protocol pain medications despite being on the highest titratable dose of buprenorphine. Therefore, we have allowed the use of oxycodone in situations where pain is uncontrolled on highest titratable doses of the drug regimen and plan to monitor the use off-protocol pain oxycodone in our study.(17, 34)

Details for the use and logistics of the OM Pain App, as well as the measure of the patient's compliance to the use of the pain app are detailed below. This study will not interfere with or cause adjustments to the standard-of-care treatments each patient will receive as determined by their multidisciplinary team of cancer doctors. To this end, basic treatment descriptions and standards are briefly described as a reference to ensure proper patient selection and to verify that patients observed on the trial will be somewhat homogeneous from a treatment perspective. A short description of possible supportive treatments that could be needed during treatment is also included. All study interventions and treatments will be administered on an outpatient basis.

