5.2 Dose Determination for Buprenorphine and Tramadol

Based on our clinical experience and earlier studies barring exceptions, the typical MEDD dose of standard-of-care regimens, such as oxycodone, morphine and fentanyl patch used in the treatment of radiation-induced mucositis can range from 20 to 90 mg. Buprenorphine is a potent opioid substitute but there is no consensus at equipotency ratio for morphine to transdermal buprenorphine. Some authors have reported that it lies somewhere between 75:1 to 100:1.(34) This makes finding the appropriate morphine equivalent daily dose (MEDD) for buprenorphine in controlling mucositis-related pain a challenging task. For our study, we used 75:1 equipotency ratio to calculate our morphine equivalent daily dose (**Table 1**). As transdermal buprenorphine is a long-acting medication, we plan to allow tramadol 50 mg (total daily dose) as needed for breakthrough pain up to 400 mg/day (total daily dose), which roughly translates to 5 mg to 40 mg MEDD. Steady-state plasma buprenorphine concentration levels are achieved by day 3, during the first application of buprenorphine. Therefore, it can be titrated after a minimum of 72 hours. We hope to evaluate the possibility of using tramadol to facilitate dose adjustment of buprenorphine. With the buprenorphine and tramadol combination, we hope to provide MEDD to patients which is comparable to other standard-of-care opioids. There is no clear consensus definition of adequate and inadequate pain relief in this setting. However, it is well known that a VAS pain score of $\leq 3/10$ is considered mild intensity pain in multiple settings. Based on some earlier studies and the titratability of TD buprenorphine dose, we have defined adequate analgesia as VAS $\leq 3/10$ for 72 hours, inadequate analgesia as VAS $> 3/10$ for 72 hours, and unbearable pain as VAS $> 3/10$ for 96 hours.(16, 17) If patients have unbearable pain (VAS $> 3/10$ x 96 hours) despite being on highest dose of the buprenorphine patch and tramadol, then, we will switch from tramadol to oxycodone for breakthrough pain and continue treatment with buprenorphine. We will titrate this combination as needed for pain control until study completion. Some authors have also shown the benefit and safety of using immediate-release oxycodone in conjunction with transdermal buprenorphine for moderate to severe pain.(35) If the pain is still uncontrolled $> 3/10$ for 72 hours, even after using oxycodone 90 mg/day with buprenorphine 20 μ g/hour, then, the patient will be taken off the study regimen. However, data monitoring will continue. Patients suffering intolerable side effects (severe constipation, vomiting, headache, pruritis, sedation, or respiratory depression, etc.) or those who wish to switch to standard-of-care oxycodone due to ineffective pain control or unclear reasons at any time during the study will be taken off study regimen. However, data monitoring through the pain app and questionnaires will continue. The dose titration schedule is illustrated in **Table 2**.

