6.2 Collection and Reporting Requirements for Adverse Events and Serious Adverse Events

6.2.1 Collection of Adverse Events

All adverse events (including SAEs) must be recorded in OnCore® and/or an adverse event log. All AEs required to be collected must be graded according to the CTCAE v5. When possible, signs and symptoms indicating a common underlying pathology should be noted as one comprehensive event. Investigator's or treating physician's assessment of AE attributions must also be documented.

AEs will be collected from the time of initiation of drug regimen to the end of follow up period. AEs will be tracked and followed until resolution, subject withdraws consent, or is lost to follow-up (including subjects who discontinue early). All adverse events collected per the protocol will be followed with appropriate medical management until they are resolved, if they are related to the study treatment, or until the investigator deems the event to be chronic.

Please see sections 6.1.1, 6.2.2 and Table 3 to identify the adverse events that need to be reported.

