8.4 Determination of Sample Size and Accrual Rate

Based on earlier studies (48) and the IMMPACT recommendations(28), a 30% or higher decrease in pain score from baseline to the end of the follow-up period is a sign of clinically meaningful efficacy of the drug regimen within a patient. A randomized trial of pregabalin for the treatment of radiotherapy-related pain in head-and-neck cancer patients (33) observed an at least 30% decrease in 33% of placebo-treated patients. This study will use a single-stage design to evaluate the hypothesis that patients treated with buprenorphine will achieve at least a 30% decrease in pain with probability exceeding 33%. Formally, the following hypotheses will be evaluated at a one-sided 5% significance level:

$$H_0: p (\geq 30\% \text{ decrease}) = 0.33 \quad \text{versus} \quad H_a: p (\geq 30\% \text{ decrease}) > 0.33.$$

With 18 subjects, the study will have at least 80% power to reject the null hypothesis if the probability of achieving at least 30% decrease in pain with buprenorphine is, in fact, 63%. The hypothesized effect is consistent with the efficacy seen with other active treatments. Specifically,

buprenorphine will be considered an acceptable pain control medication if 10 or more subjects out of the 18 experience at least 30% pain reduction. We will enroll 20 subjects to allow for 10% drop-out rate.

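### Section 8.6 does not separate PROMIS scores by the drug being taken, so the summary can misdescribe buprenorphine plus tramadol; for adverse events the gap is narrower

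*Combined protocol and SAP*

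**What the plan says.** **Endpoints (Section 8.1).** Endpoint 6, measured by weekly PROMIS, is to "Assess incidence and severity of gastrointestinal and cognitive side effects of the study drug regimen and their impact on quality of life". Endpoint 7 covers other adverse events associated with the study drug combination, graded by CTCAE.

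**Drug exposure (Sections 5.1, 5.2, 5.4).**
- If pain persists at the top dose of both drugs, tramadol is replaced by oxycodone while buprenorphine continues.
- Patients may also leave for standard-of-care oxycodone at any time. Stronger drugs are provided for if the oxycodone step fails.
- From week 8, both study drugs are tapered if pain is controlled.
- Section 5.1 expects around 20 percent of patients on the patch to be in the group that "may have inadequate pain control and require rescue off-protocol pain medications despite being on the highest titratable dose of buprenorphine".

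**Data collection.** PROMIS is weekly, up to week 12 (Section 5.10). For patients taken off the regimen, Section 5.2 says: "However, data monitoring through the pain app and questionnaires will continue". Section 6.2.1 says: "AEs will be collected from the time of initiation of drug regimen to the end of follow up period". Section 4.11 keeps procedures and event reporting going after discontinuation.

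**Analysis (Sections 8.3, 8.6).** Efficacy and safety use everyone who received at least one dose. PROMIS is reported with descriptive statistics, and then "Patient level summaries of the pain score and PRO outcomes will be created by computing area under the curve (AUC) of weekly averages". Adverse events are tabulated as counts with percentages.

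**The concern.** The endpoint names one exposure, but the data come from several. Between first dose and week 12 a patient may be on buprenorphine plus tramadol, on buprenorphine plus oxycodone, on another opioid off the regimen, or on no study drug. Section 8.6 has no on-regimen window, no rule for a switch or stop, and no split by current drug.

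PROMIS items ask only what the patient felt in the past seven days. Constipation, nausea or slowed thinking during an oxycodone week therefore enters the score that endpoint 6 reads as an effect of the study regimen. In patients who taper off, weeks without study drug pull the score the other way.

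The background (Sections 1.3 and 1.5.5) presents buprenorphine as having a more favorable side-effect profile than other opioids, and fewer gastrointestinal effects in particular. Section 5.1 adds that the weeks after radiation are the easier ones in which to see the combination's side effects. Those are also the weeks in which tapering begins and earlier switchers are already on oxycodone.

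**Working it through.** **1. The plan's own figures.** The documents give no figure for the PROMIS or adverse event analyses. The only design figure is the primary test in Section 8.4, where "the following hypotheses will be evaluated at a one-sided 5% significance level". Its null rate comes from a trial that "observed an at least 30% decrease in 33% of placebo-treated patients", and its alternative is 63%. The exact binomial for 10 or more responders of 18 gives:
- P(X ≥ 10 | p = 0.33) = 0.0405, within 5%.
- P(X ≥ 10 | p = 0.63) = 0.8165, above 80%.
- 18 / (1 − 0.10) = 20 enrolled.

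All of these reproduce, and none is touched by this point.

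**2. How likely is a switch?** The input is the roughly 20% rescue rate in Section 5.1, a general expectation applied here as an assumption.
- Expected switchers: 0.20 × 18 = 3.6, or 0.20 × 20 = 4.0.
- P(at least one): 1 − 0.8^18 = 98.2%, or 1 − 0.8^20 = 98.8%.

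**3. Earliest oxycodone step.** Table 2 has five 72-hour steps to the top dose of both drugs, then 96 hours: 5 × 3 + 4 = 19 days.

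**4. Share of patient-weeks after the switch.** PROMIS starts with treatment. The protocol anticipates treatment by the fourth week in most patients; the beginning of week 4 is assumed. Then 21 days have elapsed at start and 21 + 19 = 40 at the switch, which falls in week 6. Weeks 7 to 12 are 6 of the 9 weekly scores in weeks 4 to 12 (67% for that patient). Across 20 patients: 4 × 6 = 24 of 20 × 9 = 180, or 13.3%.

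| Start at beginning of | Switch in | PROMIS weeks | Full weeks after switch | Share at 20% switching |
|---|---|---|---|---|
| Week 3 | Week 5 | 10 | 7 | 0.20 × 7/10 = 14.0% |
| Week 4 | Week 6 | 9 | 6 | 0.20 × 6/9 = 13.3% |
| Week 5 | Week 7 | 8 | 5 | 0.20 × 5/8 = 12.5% |

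For a week 4 start with 10% to 40% switching (assumed range): 0.10 × 6/9 = 6.7% to 0.40 × 6/9 = 26.7%. In weeks 8 to 12 alone, at 20%: 4 × 5 = 20 of 20 × 5 = 100, or 20%.

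**5. Taper.** At 5 mcg per weekly step, a controlled patient on the 5 mcg/hour patch could have none after one step. A patient on 20 mcg/hour needs 20/5 = 4 steps, so has few or no patch-free weeks by week 12. The documents do not allow the overall number to be estimated.

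**6. Does another provision supply the split?**
- The per-protocol set (Section 8.3) removes patients with major violations. The oxycodone step is permitted, so it is not evidently a violation.
- The two-week treatment requirement in Section 8.6 selects patients, not weeks.
- Tabulating analgesic users, and identifying patients who need off-protocol opioids (endpoint 2), does not link those drugs to the PROMIS scores.
- For adverse events, attribution is documented (Section 6.2.1). Under Section 6.1.3, related includes events that may be related even when other factors contributed. An event on buprenorphine plus oxycodone can therefore be coded related and sit in the same row as one on buprenorphine plus tramadol.

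**The case against.** The strongest reply concerns adverse events. A reader might infer that every event on oxycodone or on no drug will be reported as an effect of the combination. The documents do not support that. Each event is attributed, and Section 6.1.3 points to unrelated where timing makes causality improbable and other drugs plausibly explain the event. Section 6.1.1 limits reporting for regulatory oversight to intervention-related events. Endpoint 7 is worded for associated events. Section 5.4 stops data monitoring during admission for intravenous pain medication. What remains for adverse events is the presentation in Section 8.6.

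The AUC sentence is also followed directly by scatterplots and Spearman correlations, so the AUC serves the correlation analysis. PROMIS reporting is the sentence before it, and week-by-week tables would be compatible with that sentence. No passage states a pooling rule; pooling is inferred from silence. This stands, but a weekly table of all treated patients would still mix drug states within each week.

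A whole-window summary in treated patients is a legitimate description of outcomes regardless of drug taken. Restricting endpoints 6 and 7 to weeks on the combination would drop the later weeks of patients who left because of constipation, vomiting or sedation, and so could flatter the regimen. That is a sound reason for reporting both views, but not for leaving out the split.

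Finally, these are descriptive secondary endpoints in a 20-patient pilot, no comparison with strong opioids is planned, and chemoradiation confounds both views. All true, and this limits the importance. Confounding by drug state, however, can be examined with data already being collected.

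**Conclusion.** The point holds for PROMIS and, more narrowly, for adverse events. As written, Section 8.6 cannot say whether a PROMIS score describes buprenorphine plus tramadol, buprenorphine plus oxycodone, another opioid or no study drug, while endpoint 6 assigns it to the regimen. The direction of the error is not known, and its size on the score scale cannot be computed because the documents give no PROMIS values by opioid.

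The 13% is an illustration, not an estimate. It rests on the general rescue figure applying here, every switcher escalating at the fastest pace, and a start at the beginning of week 4. Slower escalation lowers it; voluntary switches and weeks without study drug add to the weeks spent off the combination.

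Two further readings go too far. The documents do not let patients move to stronger opioids at any time: that wording applies to standard-of-care oxycodone, and stronger drugs are described after the oxycodone step has failed, with other combinations possible at discharge after an admission. Nor are oxycodone weeks clearly off regimen. Section 5.1 calls the oxycodone off-protocol, Table 2 in Section 5.4 lists it as a step of the titration schedule, and Section 5.2 takes the patient off the study regimen only if that step fails.

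**What to change.** In Section 8.6:

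1. Derive a weekly drug state from the drug diary and prescription-monitoring record (Section 5.12): buprenorphine plus tramadol; buprenorphine plus oxycodone; off regimen on another opioid; no study drug. Because PROMIS recall is about seven days, state how a week that spans two states is assigned.
2. Report PROMIS gastrointestinal and cognition scores by drug state, with the number of patients and patient-weeks in each.
3. Tabulate adverse events by attribution and by drug state at onset, with patient-weeks as denominator. Leave out time when monitoring was stopped for admission.
4. Keep the whole-window summary in all treated patients, labelled as regardless of drug taken. Neither view replaces the other, because weeks on the combination are selected for tolerating it.
5. State that cells will be sparse (about four switchers expected at a 20% rate) and that chemoradiation confounding remains in every state.

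Sections 5.1, 5.2 and 5.4 must also be reconciled on whether the oxycodone step counts as on or off the study regimen. This review takes no position on which is right; the analysis only needs one answer.

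The cost is a few sentences of analysis text and one derived variable from data already collected. No visit, dose rule, sample size or decision rule changes.
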